3.4.2 Secondary Outcomes (Process-Related And Clinical)

i. Guideline adherence

Number of inpatient records that contain evidence of adherence to delirium care guidelines (for the detection, assessment, management and prevention of delirium) at baseline and follow up.

- Use of 4AT screening tool
- Presence/absence of delirium risk assessment
- Use of Richmond Agitation-Sedation Scale-Pal
- Clinician-documented diagnosis of delirium
- Clinician assessment of cause/reversibility
- Presence/absence of delirium care plan
- Use of antipsychotics in relation to documented harmful/distressing behaviour towards self or others

ii. Costs

Incremental cost-effectiveness ratio quantifying the cost per PCU inpatient day affected by delirium which is avoided.

iii. Inpatient Demographics

- Age
- Sex
- Diagnosis
- Ethnicity
- Postcode (converted to IMD score at data collection)
- Primary medical condition
- Date of death (if applicable)
- Length of stay

4. Study Design

The study will be conducted in 3 related parts - Cluster RCT (cRCT) interventional study (Adaptive 'implementation-to-target' cRCT) with site PCUs randomised to the CLECC-Pal Delirium intervention or usual practice, health economic evaluation, and a parallel process evaluation (refer to [6](#) and [7](#) respectively). Information about the internal pilot (study set up feasibility and timelines) and Knowledge Exchange workshops (engagement with stakeholders about actions for future practice and policy) is included in Appendix A and B, respectively.

5. Cluster randomised-controlled trial

5.1 Site PCU inclusion criteria

1. Charitably-funded or NHS PCU providing specialist palliative care inpatient services
2. Willing to provide access to inpatient medical records
3. Capacity and capability to undertake intervention training.

5.2 Site PCU Exclusion criteria

1. Sites without capacity to support the intervention

5.3 Cluster Randomisation

There is no individual inpatient randomisation in this study. Randomisation will take place at site PCU level. Site PCUs will be randomised 1:1 via the web-based study database managed by the Hull Health Trials Team (HHTU) to receive the CLECC-Pal Delirium intervention or to continue following usual practice.

We will adopt the randomisation by minimisation approach, with three minimisation factors: number of referrals accepted annually size (as a binary), extent of specialist palliative care education/training provision (as a binary) and charity/NHS (binary).

5.4 Sample size

Based on delirium episodes in the previous feasibility study, we expect a minimum of 50 consecutive inpatient records will be required (from each site and at two timepoints) to identify 30 delirium episodes at baseline and 30 episodes at follow up (total 1200 delirium data records). We will collate data records from PCU inpatients (stopping record identification at each site as soon as 30 delirium episodes have been identified) at both timepoints (baseline and follow up) from 20 sites to obtain a total of 1200 episodes of delirium (600 baseline and 600 follow-up) to achieve a 92.3% power required to detect a 12% reduction of proportion of inpatient days affected by Delirium, at 0.05 significance level, assuming an ICC of 0.03.

5.5 Screening, Identification and Opt-Out Process

Inpatients admitted to all site PCUs will be cared for as per usual practice. There is no study specific Participant Information Sheet (PIS) for this study as eligible site PCU inpatients are not required to consent (see next section). All site PCUs will make available the study reading material (study poster, study intervention leaflet in inpatient admission packs) and, at an appropriate point in care, introduce the study to the patient (if considered clinically-appropriate) and family members/significant others. Delegated PCU staff will be responsible for checking that the consecutively admitted inpatient has not chosen to 'opt out' of research by checking the NHS National Data Opt Out register and the inpatient PCU records relating to admissions during the active study period. The Opt-out process is compliant with the National data opt-out operational policy guidance document, version 4.0, 25 Feb 2022 (compliance deadline 31-Jul-2022)⁴⁶. Screening of the opt out register and medical records will only be performed by trained and delegated site PCU staff. If the inpatient has not opted out using the NHS National Data Opt Out or expressed this preference in their medical records, a delegated site PCU team member will confirm study eligibility and document that the process was followed correctly in the records and study data collection forms.

To maximise awareness of the study and understanding of the right to opt-out, we shall collect information about languages other than English typically spoken by inpatients as part of site information process with potential site PCUs so that translated posters can be prepared in advance for other languages. As highlighted by our Public Involvement Group, this will also enable us to identify staff who speak languages other than English so that they can communicate with inpatients and family members about the study in their first language. Where a PCU inpatient is known to have poor understanding of written English or whose awareness of study posters may be impacted (e.g. due to immobility or poor eyesight that affects reading), they (and/or their consultee) will be approached by the site principal investigator (or delegate) to ensure they are fully informed of their right to opt-out.

Inpatients will not be approached to consent to take part in this study. Inpatients who have opted out of research or state they do not want to be part of the study will be excluded from data collection. The study design is that data will be collected from consecutive inpatients admitted to the site PCU. However, in the event that an inpatient opts out, data collection will skip to the next consecutive patient admitted. Ethics and CAG approvals (or equivalent in the devolved nations, if relevant) will be obtained to support this approach. If a PCU inpatient chooses to opt-out, the site principal investigator (or delegate) should note in the medical records whether the patient is opting-out of this study only or declining use of their data in all research. An opt-out log for this study will be held and maintained by trained PCU staff for the purposes of ensuring opt-out is upheld (only PCU staff will have access to this log).

To ensure inpatients are aware that the study is taking place, a study intervention leaflet will be placed in the inpatient admission pack and a poster will be provided to each site PCU. At an appropriate point in care, PCU staff will introduce the study to the patient (if considered clinically-appropriate) and family members/significant others. The poster will be clearly displayed at the PCU for 4 weeks prior to screening and sequential enrolment of inpatients to highlight to all inpatients and their visitors that the DAMPen-D Delirium II study is being conducted at the site PCU. The poster will describe what the study is doing, what data is being collected and how that data is managed. The poster will include contact details and a link to the University website for anyone wanting to find out more information about the study.

Anyone that does not wish to be involved in the study and/or have their data collected can choose to 'opt out' by informing the Site PCU team. If the patient or their carer or their consultee, does not want confidential clinical records used in the study, the site PCU staff can provide information about the study to patients/consultee and discuss opt-out consent for study data collection. No reason needs to be provided and it will not affect their ongoing medical care.

5.6 Withdrawal

As site PCUs are randomised to study intervention or usual practice, withdrawal from the study will be at site PCU level. If a site PCU inpatient or their legal guardian/conservator decides to opt out from data collection, this will be recorded on the study data log and their data will not be included in the data analysis.

Site PCU inpatients may withdraw their data from NHS England HES data collection up to the time that the study database has been closed for analysis. After this point it cannot be removed as data will have been anonymised and the NHS number will no longer be available to trace medical records.

5.7 Implementation-readiness criteria

Intervention sites must meet three 'implementation-readiness' criteria before commencing the CLECC-Pal Delirium intervention:

1. Governance approval for use of rapid delirium assessment tool (e.g. 4AT) in clinical notes
2. Lead identified for a minimum of three CLECC-Pal Delirium components (including at least one nurse)
3. PCU management support expressed for using CLECC-Pal Delirium

If these criteria are not met, intervention sites will receive strategic facilitation (structured discussion and prioritisation of how to address implementation barriers; identification of individual motivations and support for exploring how to meet individual goals; identification of organisational drivers and support to explore alignment of these with delirium guideline implementation and use of CLECC-Pal Delirium).

5.8 Data collection

Site PCU inpatient data (see Table 2) will be collected by a study researcher based at the University of Hull, not by site PCU staff. If any case notes cannot be obtained or accessed for any reason, this will be recorded by the researcher on the study data collection forms. All outcome measures are considered to be part of usual practice and no additional questionnaires or tools will be included as part of the study intervention.

Demographic data will be recorded in a way that decreases identifiability of the PCU inpatients (e.g. recording length of stay rather than date of admission and discharge). Postcode will be converted to an IMD score at the point of extraction.

We shall report the percentage of clinical records where information about each of these actions is recorded. Where a person experiences multiple episodes of delirium within one admission these

will be recorded on separate CRF and treated as separate episodes. Where judgements about what to record on the CRF need to be made, justification for these will be recorded on the form.

Any uncertainty about how the information in the case-notes should be recorded on the pro-forma will be discussed with a clinician and justification for the final decision recorded on the pro-forma.

Our 'expanded' version of the instrument will include questions about other actions to support delirium assessment, management and prevention that may be recorded in the notes. We shall report the percentage of clinical records where information about each of these actions is recorded. Where a person experiences multiple episodes of delirium within one admission these will be recorded on separate pro-forma and treated as separate episodes. Where judgements about what to record on the pro-forma need to be made, justification for these will be recorded on the form. Any uncertainty about how the information in the case-notes should be recorded on the pro-forma will be discussed with a clinician and justification for the final decision recorded on the pro-forma.

Table 2: Data Collection (Completed By HHTU Study Researchers)

Primary Endpoint	Measure	How	Timepoints
To evaluate the effectiveness of CLECC-Pal Delirium intervention compared to usual practice to reduce the total proportion of inpatient days affected by delirium in PCUs, in a fully powered cRCT.	For patients who experience delirium during PCU admission, the proportion of inpatient days affected by delirium, calculated as the number of days they experience delirium divided by their total number of inpatient days	Data extraction from 
 • Paper • Medical records e.g. SystmOne/EMIS • NHS England HES data 	Two timepoints: Baseline 50 consecutively admitted inpatients who completed their inpatient stay during the time period from display of poster to start of intervention Note: As this is information entered into the inpatient records on the day of events, baseline data can be collected retrospectively at any point during the study Follow up 50 consecutively admitted inpatients who completed their inpatient stay from the beginning of the seventh calendar month after starting the intervention (in the intervention arm) or continuing usual practice (in the control arm)
Secondary Endpoints	Measure	How	Timepoints
To identify adherence to delirium care guidelines (for the detection, assessment, management, and prevention of delirium) at baseline and follow up 
 • 4AT screening tool • Delirium risk assessment • Richmond Agitation-Sedation Scale • Clinician-documented diagnosis of delirium • Clinician assessment of cause/reversibility • Use of antipsychotics in relation to documented harmful/distressing behaviour towards self or others • Delirium care plan • Medication review 	Present in the records? Yes / No	Data extraction from: 
 • Paper records • Medical records e.g. SystmOne/EMIS • NHS England HES data 	As above
To explore symptom burden and functional status during inpatient admissions 
 • Integrated Palliative care Outcome Scale (IPOS) • Australian-modified Karnofsky Performance Scale (AKPS) 	Tool score		
To evaluate the cost-effectiveness of CLECC-Pal Delirium compared to usual practice on reducing the proportion of in-patient days affected by delirium in PCUs	Cost		
Age, Sex, Primary medical condition, Ethnicity, Postcode (converted to IMD score at data collection), Primary medical condition, Date of death (if applicable), Length of stay.	Not applicable		

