5.9 Statistical Analysis

5.9.1 Sample Size

Based on delirium episodes in the feasibility study, a minimum of 50 consecutive patient records are required (from each site, at each timepoint) to identify each sample of 30 delirium episodes. This figure will be revisited during the internal pilot.

The study requires 30 inpatients with a delirium episode from each of 20 PCUs

Size of cluster=30

Number of PCU clusters for randomisation=20

Total number of inpatient records required = 2000

Number of delirium episodes inpatient records required = 1200

Intraclass correlation coefficient (ICC) is generally smaller for clinical outcomes than for process outcomes, with a median value of 0.03. Our goal is to achieve 12% reduction (from 70% to 58%), leading to a moderate effect size of 0.4. No attrition rate is expected since each PCU will collect data from cross sectional cohorts (baseline and follow-up). The outlined sample size will provide 92.3% power to detect a 12% reduction of proportion of days affected by delirium, at 0.05 significance level, assuming an ICC of 0.03.

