9.1 Data Collection

Clinical record data will be collected and entered into a secure web-based electronic data capture system provided by the Hull Health Trials Unit (HHTU). See [Figure 1](#) for data flow summary.

The data collection forms will collate data to enable us to assess whether case-note recorded symptoms of delirium can be linked to time-points during the person's admission when actions around delirium assessment, management and prevention (consistent with guidelines) did or did not take place. Also included in the data collection form are questions about other actions undertaken to support delirium assessment, management and prevention that may be recorded in the notes.

Where an inpatient experiences multiple episodes of delirium within one admission, each episode will be treated as a separate episode. A period of five days without signs of delirium will be used to distinguish separate episodes.

Where judgements about what to record on the CRF need to be made, justification for these will be recorded. Any uncertainty about how the information in the medical records should be recorded will be discussed with a clinician and justification for the final decision recorded on the eCRF. We will also collect more detailed information on emergency and admitted inpatient care for the main trial and health economic analyses via NHS England to link records to Hospital Episode Statistics (HES) data.

To protect the identity of individuals, a separate linkage database (the patient information database) will be used. This database will securely store the identifiers, NHS numbers and dates of birth, and will generate a unique study ID for each individual. The study ID will then be used in the clinical record database to maintain data integrity while safeguarding personal identifiers. Additionally, the linkage database will be used to generate a list of identifiers to be shared with NHS England for linkage with Hospital Episode Statistics (HES) data. By separating direct identifiers from clinical records and relying on study IDs, this approach will ensure robust privacy protection while minimising the use of identifiable information.

To minimise the length of time that patient identifiable information is held on the patient information database, separate DARS requests for baseline and post-implementation data will be requested. At each timepoint, the linkage database will only be required until the

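### Record identification stops at 30 delirium episodes per site, but the outcome and the stated sample size need 30 distinct inpatients, so the 92.3% power is not assured

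*Protocol*

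**What the plan says.** **Outcome.** Section 3.4.1, the Trial Summary and Table 2 define one value per inpatient with delirium: the days that the inpatient experiences delirium, divided by that inpatient's total inpatient days.

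**Sample size.** Section 5.9.1 states: "The study requires 30 inpatients with a delirium episode from each of 20 PCUs". The same section also speaks of samples of 30 delirium episodes, and its line for the total of 1200 names episodes and inpatient records together. So it uses both units.

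**Stopping rule.** Section 5.4 has "stopping record identification at each site as soon as 30 delirium episodes have been identified", at baseline and again at follow-up, towards 1200 episodes in all. The Sample Size Rationale in the Trial Summary repeats the rule.

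**Repeat episodes.** Section 5.8 says that "multiple episodes of delirium within one admission these will be recorded on separate pro-forma and treated as separate episodes". Section 9.1 adds the dividing rule: "A period of five days without signs of delirium will be used to distinguish separate episodes".

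**Model.** Section 5.9.3 specifies two-level modelling with PCU as cluster. It does not name the lower-level unit.

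**The concern.** The two counts, 30 inpatients and 30 episodes, agree only if nobody has a second episode in the same stay. Sections 5.8 and 9.1 provide for exactly that case. Each recurrence uses up one of a site's 30 places without adding a new inpatient.

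This decides which records are collected, so it cannot be left to the analysis. A statistical analysis plan can add up a patient's episode forms. It cannot bring back inpatients who were never identified because the site had already reached 30 episodes.

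A second, conditional issue follows. The protocol does not say how several episode forms become one value for the primary analysis. If each form became a row, a patient's delirium days would be divided between rows that share one length of stay. The average over rows would then depend on how often episodes recur, as well as on how many days are affected.

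**Working it through.** **Inputs from section 5.9.1:** 20 PCUs (10 per arm under the 1:1 allocation in section 5.3); cluster size 30; a fall from 70% to 58%, "leading to a moderate effect size of 0.4"; "at 0.05 significance level, assuming an ICC of 0.03". Sidedness is not stated; two-sided is assumed. The implied SD is 0.12/0.4 = 0.30.

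**Step 1: reproduce the stated power.**
- Design effect = 1 + (30 − 1) × 0.03 = 1.87
- Effective number per arm = 10 × 30 / 1.87 = 160.4
- Noncentrality = 0.4 / √(2/160.4) = 3.58
- Two-sided noncentral t with 20 − 2 = 18 df: power 92.3%

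This matches "The outlined sample size will provide 92.3% power". A normal approximation gives 94.8%, and a cluster size of 60 (both timepoints pooled) gives 97.6%; neither matches. The stated figure therefore rests on 30 independent units per PCU at one timepoint.

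**Step 2: stop at 30 episodes instead.** With r episodes per inpatient with delirium, 30 episodes come from m = 30/r distinct inpatients. The protocol gives no r, so the values above 1 are assumptions. The outcome is taken as one value per inpatient.

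| r | Inpatients per PCU (m) | Design effect 1 + (m − 1) × 0.03 | Effective n per arm | Power |
|---|---|---|---|---|
| 1.0 | 30.0 | 1.87 | 160.4 | 92.3% |
| 1.1 | 27.3 | 1.79 | 152.5 | 91.0% |
| 1.2 | 25.0 | 1.72 | 145.3 | 89.7% |
| 1.5 | 20.0 | 1.57 | 127.4 | 85.5% |
| 2.0 | 15.0 | 1.42 | 105.6 | 78.5% |

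**Step 3: only if episode forms became rows.** Take a 20-day stay with episodes of 6 and 5 days. The inpatient's value is 11/20 = 55%; the two rows would be 30% and 25%.

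Now suppose that every patient with delirium in both arms is truly at 70%, so there is no treatment effect, and that a share q of them has two equal episodes, entered as two rows of 35%. Then

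row mean = [(1 − q) × 0.70 + 2q × 0.35] / (1 + q) = 0.70 / (1 + q).

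- q = 10%: 63.6%
- q = 20%: 58.3%
- 10% in one arm and 20% in the other: spurious difference 63.6 − 58.3 = 5.3 points, against a target of 12
- 10% v 15%: 63.6 − 60.9, about 2.8 points
- 10% v 12%: 63.6 − 62.5, about 1.1 points
- Equal q in both arms: no spurious difference

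**The case against.** The strongest reply is that the separate forms are only a recording rule. In section 5.8 the rule sits beside the reporting of care actions, and sections 2.1 and 9.1 say that the forms link symptoms to the times of those actions. Section 3.4.1 gives one proportion per inpatient, so the natural lower level of the model is the inpatient, and adding up the forms can be left to an analysis plan that is not at hand. This stands. A reader might infer that the plan already splits each patient's outcome, but no section computes a proportion per episode.

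Three other strong readings also fail.

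- **Standard errors too small.** A reader might infer that a model without a patient level understates the standard error. Allocation is by PCU and patients are nested in PCUs, so the PCU component largely absorbs within-patient correlation for the treatment effect. In simulations under no effect (20 PCUs of about 30 rows, ICC 0.03, SD 0.30, 18 df, 8,000 runs), with 0%, 10% or 20% of patients entered as two identical rows, type I error was 4.8%, 4.7% and about 5%.
- **Level shift read as bias.** The row mean at 20% recurrence lies 11.7 points below 70%, close to the 12-point target. That is a shift in level. It biases the comparison only to the extent that recurrence differs between arms.
- **Recurrence inferred from the feasibility figures.** Section 1 gives 23% with delirium at admission and 41% during admission. If 41% were the total, 50 records would hold 20.5 inpatients with delirium, and 30 episodes would mean 30/20.5 = 1.46 episodes each (power 86.0%). If the two figures add up, 64% of 50 is 32 inpatients and no recurrence is needed. The text does not settle which applies.

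The five-day rule also limits recurrence. Two episodes need a stay of at least 1 + 5 + 1 = 7 days, and a two-episode patient at 70% needs at least 5/0.30 = 16.7 days. Section 5.9.3 expects two deaths for each discharge, and shorter stays in patients who die soon after admission. This makes high recurrence less likely but does not exclude it.

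None of this answers the stopping rule, which still counts episodes.

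**Conclusion.** The conflict of units is in the text and should be fixed. As written, a site may stop with fewer than 30 distinct inpatients with delirium, which is below the number behind the stated power. The power calculation itself is correct on its own inputs.

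The loss is about 1 to 3 points of power at 1.1 to 1.2 episodes per inpatient and about 7 points at 1.5. These rates are assumptions, so the true size is unknown. The calculation also takes the protocol's ICC of 0.03 and effect size of 0.4 as given.

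The possible bias is conditional on two things that the protocol does not state: episode forms entering the model as rows, and recurrence differing by arm. The 5.3-point figure illustrates what the wording leaves open and is not a prediction.

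**What to change.** 1. In the Trial Summary's Sample Size Rationale and in sections 5.4 and 5.9.1, use one unit: the inpatient admission with at least one delirium episode.
2. Stop record identification at 30 such inpatients per site and timepoint, and restate the total as 1200 inpatients with delirium (600 at baseline, 600 at follow-up).
3. In section 5.8 or 5.9.3, state that delirium days are summed over all episodes in the stay and divided by total inpatient days, giving one row per admission for the primary analysis. Keep the episode forms for description.

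The cost is a wording change and slightly more records where patients recur. If 50 records yield 30 episodes, reaching 30 inpatients takes about 50 × 1.1 = 55 records at 1.1 episodes per inpatient, or 50 × 1.2 = 60 at 1.2. The internal pilot, where section 5.9.1 already plans to revisit the figure of 50, can supply the recurrence rate. The change should be made before any site closes its record identification.
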